2.1 Primary Objectives

Immunogenicity

Tdap immunogenicity

- To demonstrate the non-inferiority of the humoral immune response to the Tdap booster dose concomitantly administered with the first dose of CYD dengue vaccine as compared to sequential administration, measured 28 days after Tdap booster dose*

CYD dengue vaccine immunogenicity

- To demonstrate the non-inferiority of the humoral immune response to the first dose of CYD dengue vaccine concomitantly administrated with Tdap compared to sequential administration, measured 28 days after the first dose of CYD dengue vaccine*

The endpoints for the primary objectives are presented in Section 4.1.

* Providing that the number of evaluable subjects allows a global power of at least 80% (otherwise analyses will be descriptive).

2.2 Secondary Objectives

CYD dengue vaccine immunogenicity

- To demonstrate the non-inferiority of the humoral immune response of 3 doses of CYD dengue vaccine with the first dose concomitantly administered with Tdap as compared to sequential administration, measured 28 days after the third dose of CYD dengue vaccine*
- To describe the humoral immune response at baseline and 28 days after the first and third doses of CYD dengue vaccine in each and any group*.

* Objectives on the 3rd dose are not applicable due to the early termination of study (cf. section 5.7)

Tdap immunogenicity

- To describe the humoral immune response of Tdap vaccine at baseline and 28 days after concomitant administration with the first dose of CYD dengue vaccine as compared to the sequential administration, in each and any group

Safety

Tdap and CYD dengue vaccine safety

- To describe the safety of the CYD dengue vaccine and of the Tdap booster dose after each and any injection in each group

The endpoints for the secondary objectives are presented in Section 4.2.

3 Description of the Overall Trial Design and Plan

3.1 Trial Design

This is a Phase IIIb, randomized, open label, multicenter study in 688 healthy subjects aged 9 to 60 years in the Philippines.

Subjects were to receive the CYD dengue vaccine according to a 3-dose schedule, given 6 months apart. A booster dose of Tdap vaccine (Adacel®) was to be administered either concomitantly to or before (sequential administration) the first dose of CYD dengue vaccine.

Subjects were to be randomized according to a 1:1 ratio into one of the 2 following groups with stratification on age (9 to 11 years, 12 to 17 years, 18 to 45 years and 46 to 60 years):

- **Group 1:** subjects were to be administered the first dose of CYD dengue vaccine concomitantly with the booster dose of Tdap vaccine at the second visit (V02; M1)
- **Group 2:** subjects were to receive Tdap vaccine at the first visit (V01; D0), and then CYD dengue vaccine 28 days later at the second visit (V02; M1)

The stratification was to be considered in order to balance the potential difference in terms of booster response by age group for the pertussis antigens (PT, FHA, PRN and FIM2+3).

Since the CYD dengue is to be administered according to a 3-dose schedule, given 6 months apart, initial trial design included administration of the second and third doses of CYD dengue vaccine at V04 (Month 7 [M7] and at V06 (M13) in all subjects.

At the time of study hold linked to the recommendation from IDMC not to vaccinate seronegative individuals anymore based on the results of the exploratory case-cohort study, all but 19 subjects (from both, Group 1 and Group 2) did receive dose 2 of the CYD dengue vaccine as planned. Following the IDMC recommendations, Sanofi Pasteur paused all vaccinations in CYD66 study, determined baseline serostatus and the Principal Investigators have communicated serostatus information to subjects already included in the study. In addition, the study protocol was amended to reflect the IDMC recommendations. The Sponsor has not received any feedback nor approval for the protocol amendment from Philippines FDA and has therefore decided to put an end to the CYD66 study with a last visit (which served as termination visit) of the subjects in order to inform them of the end of the study and to perform the last safety follow up. As a consequence, no more CYD dengue vaccine were administered to any subjects included in the study since the study hold. More details will be mentioned in the CSR

Blood samples (BL) collected before dose 1 of the vaccine at V02 were used to determine dengue serostatus at baseline. Dengue serostatus was determined using the Dengue 50% plaque reduction neutralization test (PRNT50).

3.2 Trial Plan

A schedule of assessments and study vaccinations was provided in the table of study procedures (Table 3.1).

All information collected during the study visits should be reported into the source documents. Some of the following information was to be recorded in the electronic case report form (eCRF).

Table 3.1: Study procedures as per initial study protocol

Phase IIIb Trial, 4 Vaccinations, 7 Visits and 3 or 4 Blood Samples (depending on group allocation), 19 Months Duration Per Subject. One Safety Follow-up Phone Call (PC) will be given 6 months after the last injection and 3 Interim phone calls will be given during the 6-month period after each CYD dengue vaccine injection (approximately 3 months after vaccination). .

Visit Number (V)	V01	V02	V03	V04	V05	V06†††	V07†††	Phone call***†††††
Trial Timelines* (Days/Months)	D0	M1 (V01+28D)	M2 (V02+28D)	M7 (V04+28D)	M8 (V06+28D)	M13 (V06+28D)	M14 (V06+28D)	Last vaccination+6M
Time Windows (Days)	+14	+14	+14	+20	+14	+20	+14	+30
Assent or Informed Consent	X							
Inclusion/Exclusion Criteria	X	X (Group 1)						
Contraindication	X (Group 2)	X		X			X	
Significant Medical History	X							
History of Dengue Infection/Vaccination	X							
Temperature	X (Group 2)	X		X			X	
Physical Examination†	X	X	X	X	X	X	X	X
Urine Pregnancy Test‡	X (Group 2)	X		X			X	
Demography/Body Stature	X							
Randomization	X							
Blood Sampling (BL) for Immunogenicity††								
T, D, PT, FHA, PRN, and FIM2+3	BL (Group 2)	BL	BL (Group 1)				BL	
Dengue Serotypes 1, 2, 3, and 4		BL	BL					
Tdap Vaccination §	X (Group 2)	X (Group 1)						
CYD dengue Vaccination §		Dose 1		Dose 2		Dose 3		
Post-injection phone calls (PC)**								Interim phone calls will be given during the 6-month period after each CYD dengue vaccine injection. The last phone call will be held 6 months after the last injection.
30-Min. Observation Period	X (Group 2)	X (Group 2)		X				
Injection Site and Systemic Events Collected***				X	X	X	X	X

Visit Number (V)	V01	V02	V03	V04	V05	V06†††	V07†††	Phone call***†††
Diary Card (DC) DC Provided	X (Group 1 for SAE only, and Group 2)	X	X	X	X	X	X	
DC Collected		X		X		X	X	
Memory Aid (MA) MA Provided							X	
MA Checked							X	
Concomitant Therapy†‡	X	X	X	X	X	X	X	X
Telephone Contact								
Blood Sampling (BL) for virological confirmation of hospitalized suspected dengue cases§§	All acute febrile illness with diagnosis of hospitalized suspected dengue case within the first 5 days after fever onset, anytime throughout the trial period							
SAEs and AESIs collected***								
Termination Record§§§							X	

AESI: AE of special interest; BL: blood sample; D: Day; M: Month; MA: Memory Aid; SAE: Serious adverse event; V: Visit

* Timelines must be calculated based on the date of vaccination, not the date of visit.

** Interim phone calls will be given during the 6-month period after each CYD dengue vaccine injection: 3 months after Visit 2 (PC1: M4 [M1 + 3 months]), 3 months after Visit 4 (PC2: M10 [M7 + 3 months], and 3 months after Visit 6 [PC3: M16 M13 + 3 months]). The last PC will be held 6 months after the last vaccination.

† Physical examination will be performed if necessary, based on the health status of the subject.

‡ For female subjects of childbearing potential (e.g., a female subject who has reached menarche).

§ CYD and Tdap will be administered in 2 different sites, with the CYD dengue vaccine administered in one deltoid and Tdap in the other deltoid

§§ Concomitant therapy and ongoing medication will be collected for Days 0–28 after each injection only

§§§ Blood samples planned during vaccination visits will be taken before vaccination

†† Solicited injection site reactions will be collected for Days 0–7 after each injection. Solicited systemic reactions will be collected for Days 0–14 after each injection. Unsolicited events will be collected for Days 0–28 after each injection.

††† In such case, 1 unplanned acute blood sample (approximately 3 mL) will be collected for virological confirmation of hospitalized suspected dengue case SAEs will be reported throughout the study and AESIs will be collected in defined time windows according to the type of AESI (hypersensitivity/allergic reactions [serious or not] within 7 days after each CYD dengue vaccine injection, serious viscerotropic within 30 days after each CYD dengue vaccine injection, serious dengue cases requiring hospitalization (hospitalized VCD case) will be reported during the entire study).

*** Termination form will be completed

††† Due to early termination of the study, V06 and V07 were not performed. Phone call 6 month after last vaccination were replaced by a last safety visit regardless the time from last vaccination §§§ Due to early termination, of the study, V06 and V07 were not performed. Phone call 6 month after last vaccination were replaced by a last safety visit regardless the time from last vaccination

4 Endpoints and Assessment Methods

4.1 Primary Endpoints and Assessment Methods

4.1.1 Immunogenicity

4.1.1.1 Immunogenicity Endpoints

See Section 9.1.1.1 of the protocol version 1.0 dated 17 March 2016.

4.1.1.2 Immunogenicity Assessment Methods

See Section 9.1.1.2 of the protocol version 1.0 dated 17 March 2016.

4.1.2 Safety

There are no primary objectives for safety.

4.1.3 Efficacy

There are no primary objectives for efficacy.

4.2 Secondary Endpoints and Assessment Methods

4.2.1 Immunogenicity

4.2.1.1 Immunogenicity Endpoints

See Section 9.2.1.1 of the protocol version 1.0 dated 17 March 2016.

4.2.1.2 Immunogenicity Assessment Methods

See Section 9.2.1.2 of the protocol version 1.0 dated 17 March 2016.

4.2.2 Safety

4.2.2.1 Safety Endpoints

See Section 9.2.2.2 of the protocol version 1.0 dated 17 March 2016.

4.2.2.2 Safety Assessment Methods

See Section 9.2.2.3 of the protocol version 1.0 dated 17 March 2016.

4.2.3 Efficacy

There are no secondary objectives for efficacy.

4.3 Observational Endpoints and Assessment Methods

There are no observational objectives in this study.

4.4 Derived Endpoints: Calculation Methods

4.4.1 Safety

4.4.1.1 Solicited Reactions

The solicited period for solicited injection site reactions is from Day (D) 0 to D7 and from D0 to D14 for solicited systemic reactions.

Table 4.1, Table 4.2, and Table 4.3 present, respectively, the injection site reactions and systemic reactions that are prelisted in the DCs and CRF for the different age group, together with the intensity scales.

Table 4.1: Solicited injection site reactions: terminology, definitions, and intensity scales for subjects aged 9 to 11 years

CRF term (MedDRA lowest level term [LLT])	Injection site pain	Injection site erythema	Injection site swelling
DC term	Pain	Redness	Swelling
Definition		Presence of a redness including the approximate point of needle entry	Swelling at or near the injection site Swelling or edema is caused by a fluid infiltration in tissue or cavity and, depending on the space available for the fluid to disperse, swelling may be either soft (typically) or firm (less typical) to touch and thus can be best described by looking at the size of the swelling
Intensity scale*	Grade 1: Easily tolerated Grade 2: Sufficiently discomforting to interfere with normal behavior or activities Grade 3: Incapacitating, unable to perform usual activities	Grade 1: > 0 to < 25 mm Grade 2: ≥ 25 to < 50 mm Grade 3: ≥ 50 mm	Grade 1: > 0 to < 25 mm Grade 2: ≥ 25 to < 50 mm Grade 3: ≥ 50 mm

* For the subjective reaction of pain, subjects or parents/legally acceptable representatives have recorded the intensity level (Grade 1, 2, or 3) in the DC. For the measurable reactions of redness and swelling, they have recorded just the size of the reaction, and the classification as Grade 1, 2, or 3 has been assigned at the time of the statistical analysis.

Table 4.2: Solicited injection site reactions: terminology, definitions, and intensity scales for subjects aged >= 12 years for all subjects

CRF term (MedDRA LLT)	Injection site pain	Injection site erythema	Injection site swelling
DC term	Pain	Redness	Swelling
Definition		Presence of a redness including the approximate point of needle entry	Swelling at or near the injection site Swelling or edema is caused by a fluid infiltration in tissue or cavity and, depending on the space available for the fluid to disperse, swelling may be either soft (typically) or firm (less typical) to touch and thus can be best described by looking at the size of the swelling
Intensity scale*	Grade 1: No interference with activity Grade 2: Some interference with activity Grade 3: Significant; prevents daily activity	Grade 1: ≥ 25 to ≤ 50 mm Grade 2: ≥ 51 to ≤ 100 mm Grade 3: > 100 mm	Grade 1: ≥ 25 to ≤ 50 mm Grade 2: ≥ 51 to ≤ 100 mm Grade 3: > 100 mm

* For the subjective reaction of pain, subjects/parents/legally acceptable representatives have recorded the intensity level (Grade 1, 2, or 3) in the DC. For the measurable reactions of redness and swelling, they have recorded just the size of the reaction, and the classification as Grade 1, 2, or 3 has been assigned at the time of the statistical analysis

Table 4.3: Solicited systemic reactions: terminology, definitions, and intensity scales

CRF term (MedDRA LLT)	Fever	Headache	Malaise	Myalgia	Asthenia
DC term	Temperature	Headache	Feeling unwell	Muscle aches and pains	Weakness
Definition	Elevation of temperature to $\geq 38.0^{\circ}\text{C}$ ($\geq 100.4^{\circ}\text{F}$)	Pain or discomfort in the head or scalp. Does not include migraine.	General ill feeling. Malaise is a generalized feeling of discomfort, illness, or lack of well-being that can be associated with a disease state. It can be accompanied by a sensation of exhaustion or inadequate energy to accomplish usual activities.	Muscle aches and pains are common and can involve more than one muscle at the same time. Muscle pain can also involve the soft tissues that surround muscles. These structures, which are often referred to as connective tissues, include ligaments, tendons, and fascia (thick bands of tendons). Does not apply to muscle pain at the injection site which should be reported as injection site pain.	Generalized weakness.
Intensity scale*	Grade 1: $\geq 38.0^{\circ}\text{C}$ to $\leq 38.4^{\circ}\text{C}$, or $\geq 100.4^{\circ}\text{F}$ to $\leq 101.1^{\circ}\text{F}$ Grade 2: $\geq 38.5^{\circ}\text{C}$ to $\leq 38.9^{\circ}\text{C}$, or $\geq 101.2^{\circ}\text{F}$ to $\leq 102.0^{\circ}\text{F}$ Grade 3: $\geq 39.0^{\circ}\text{C}$ or $\geq 102.1^{\circ}\text{F}$	Grade 1: No interference with activity Grade 2: Some interference with activity Grade 3: Significant; prevents daily activity	Grade 1: No interference with activity Grade 2: Some interference with activity Grade 3: Significant; prevents daily activity	Grade 1: No interference with activity Grade 2: Some interference with activity Grade 3: Significant; prevents daily activity	Grade 1: No interference with activity Grade 2: Some interference with activity Grade 3: Significant; prevents daily activity

* For all reactions but fever, subjects or parents/legally acceptable representatives have recorded the intensity level (Grade 1, 2, or 3) in the DC. For fever, they have recorded the body temperature, and the classification as Grade 1, 2, or 3 has been assigned at the time of the statistical analysis.

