4.4.1.1.3 Presence

Presence of solicited reactions will be computed based on daily records during the solicited period. For any specific period, a subject would be considered to have a reaction if the intensity is greater than or equal to Grade 1 for at least one day during that period. If no data is recorded and the presence recorded by the Investigator is different from "No", the presence will be considered as "Missing."

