5.1.2.2 Statistical Methods

Non-inferiority on CYD dengue vaccine after 3 doses

Analysis on the 3rd dose are not applicable due to the early termination of the study (cf. section 5.7)

Descriptive analysis on CYD dengue vaccine and Tdap vaccine immunogenicity*

No hypotheses will be tested. Immunogenicity point estimates and their 95% CI will be presented for each and any group and by baseline dengue status, before and after the first injections for CYD dengue vaccine and before and after the booster vaccination for Tdap.

A complementary analysis on CYD dengue vaccine and Tdap vaccine immunogenicity after each dose will be conducted for each and any group according to the age groups (9 to 11 years, 12 to 17 years, 18 to 45 years and 46 to 60 years).

* Analysis on the 3rd dose are not applicable due to early termination of study (cf. section 5.7)

In addition, the booster response against pertussis components (PT, FHA, PRN, and FIM2+3) will be calculated based on Ab concentration rises between pre- and post-vaccination defined as:

- A post-vaccination Ab concentration $\geq 4 \times$ the lower limit of quantification (LLOQ) when pre-vaccination concentration is $< \text{LLOQ}$
- A post-vaccination Ab concentration $\geq 4 \times$ pre-vaccination Ab concentration when pre-vaccination concentration is $\geq \text{LLOQ}$ but $< 4 \times \text{LLOQ}$
- A post-vaccination Ab concentration $\geq 2 \times$ pre-vaccination Ab concentration when pre-vaccination concentration is $\geq 4 \times \text{LLOQ}$

Safety

All analyses will be descriptive; no hypotheses will be tested. Safety will be assessed for all subjects after the booster dose of Tdap vaccine and after each and any dose of CYD Dengue vaccine and by baseline dengue status.

A complementary analysis will be conducted for each group according to the age groups (9 to 11 years, 12 to 17 years, 18 to 45 years and 46 to 60 years).

A complementary analysis after the first CYD dengue vaccine will be conducted for each and any group in the non-immune or undetermined dengue subjects at baseline.

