5.2.5 Populations Used in Analyses

The main immunogenicity analyses (non-inferiority tests) will be performed on the per protocol analyses sets PPT and PPC respectively for Tdap and CYD dengue vaccine comparisons For Tdap and will be confirmed on the FAS (only Dengue Immune subjects for CYD dengue vaccine). The subjects will be analyzed by the group to which they were randomized.

All other immunogenicity analyses will be performed on the FAS by baseline dengue status. Subjects will be analyzed by the vaccine group to which they were randomized.

The SafAS will be performed on the safety analysis set by baseline dengue status. Subjects will be analyzed according to the vaccine they actually received.

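### All-ages and by-serostatus rates of redness and swelling mix two size definitions (above 0 mm at 9-11 years, 25 mm from 12 years); the SAP plans no common cut-off

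*SAP*

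**What the plan says.** SAP 4.4.1.1 gives two intensity scales for erythema and swelling, identical to Protocol Tables 9.1 and 9.2. At 9-11 years (Table 4.1) the lowest category is "Grade 1: > 0 to < 25 mm" and Grade 3 starts at 50 mm. At 12 years and over (Table 4.2) the lowest category is "Grade 1: ≥ 25 to ≤ 50 mm" and Grade 3 means more than 100 mm. The older scale has no grade below 25 mm.

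Under SAP 4.4.1.1.3, "a subject would be considered to have a reaction if the intensity is greater than or equal to Grade 1" on at least one day of the period. Grades are assigned at analysis, since for redness and swelling "they have recorded just the size of the reaction" in the diary card.

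SAP 5.1.2.2 summarises safety for all subjects after the Tdap dose and "after each and any dose of CYD Dengue vaccine and by baseline dengue status". SAP 5.2.5 adds: "The SafAS will be performed on the safety analysis set by baseline dengue status". SAP 5.7 lists the presentation by serostatus among the changes to the planned analyses. Separately, "A complementary analysis will be conducted for each group according to the age groups". The SAP states no summary on one threshold for all ages, and no safety summary by serostatus within age group or adjusted for age.

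**The concern.** A table headed as the rate of redness should count the same thing in every subject in its denominator. Here a 1-24 mm reaction is an event in a child of 9-11 and a non-event in anyone older. The grades also diverge at the upper end: a 50 mm reaction is Grade 3 at 11 years and Grade 1 at 12. Time to onset, days of occurrence and ongoing status are all derived from the same grades, so they inherit the split.

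Two things are at stake. First, the all-ages rate has no plain meaning: it is a weighted average of two different proportions. Secondly, the weights depend on age mix. Where two columns of a table have different age mixes, the rates can differ even if the skin response is the same. Serostatus is not a randomised factor, so nothing in the design guarantees equal age mixes in those two columns.

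**Working it through.** **Inputs from the documents**
- Planned age mix: 86 of 344 per group in each of four age strata (SAP 5.5), so 86/344 = 25% aged 9-11 in each group.
- Serostatus after the first dengue injection: 629 seropositive and 47 seronegative of 676 (SAP Introduction). 629/676 = 93.0% and 47/676 = 7.0%, as stated.
- The only stated safety sample-size figure is a 95% chance of seeing an event with incidence above 0.87% when N = 344. It reproduces: 1 − (1 − 0.0087)^344 = 0.9505. It is not in dispute here.

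**Inputs assumed**, because the documents give no reaction sizes and no age-by-serostatus table
- a = proportion with any measurable reaction (above 0 mm); b = proportion with 25 mm or more. Both are taken as equal at every age, to isolate the effect of the definitions.
- s = share aged 9-11 among the 47 seronegatives. With 25% of 676 = 169 aged 9-11 in all, the share among seropositives is p = (169 − 47s)/629.

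**Step 1: pooled rate.** Reported rate = 0.25a + 0.75b.

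| a (any) | b (25 mm or more) | Reported |
|---|---|---|
| 5% | 1% | 2.0% |
| 10% | 2% | 4.0% |
| 20% | 5% | 8.75% |
| 30% | 10% | 15.0% |

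The reported figure matches neither column in any row.

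**Step 2: Group 1 against Group 2.** Both groups carry the same 25/75 weights, so the difference is 0.25(a₁ − a₂) + 0.75(b₁ − b₂). This is zero when reaction sizes are distributed alike in the two groups. The mix alone creates no difference between groups.

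**Step 3: seronegative minus seropositive.** Each rate is (share aged 9-11) × a + (1 − share) × b, so the artefactual difference is (s − p)(a − b). With a = 20%, b = 5% and no true difference:

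| s | p | Seronegative | Seropositive | Difference (points) |
|---|---|---|---|---|
| 10% | 26.1% | 6.5% | 8.9% | −2.4 |
| 25% | 25.0% | 8.75% | 8.75% | 0.0 |
| 50% | 23.1% | 12.5% | 8.5% | +4.0 |
| 75% | 21.3% | 16.25% | 8.2% | +8.1 |
| 100% | 19.4% | 20.0% | 7.9% | +12.1 |

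Over s from 10% to 100%, the difference runs from −0.6 to +3.2 points with a = 5%, b = 1%, and from −3.2 to +16.1 points with a = 30%, b = 10%.

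**Step 4: precision.** In 47 subjects, 4.0 points is about 47 × 0.040 = 1.9 people. An observed 5/47 (10.6%) has an exact 95% interval of 3.5% to 23.1%.

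**Step 5: common cut-off.** If every subject is counted on the same threshold, each stratum's rate is a (or b) whatever its age mix, so the artefact is zero in every row above.

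**The case against.** The age-specific scales come from the protocol and the SAP applies them faithfully, so there is no contradiction between the documents. All safety analyses are descriptive, and no test of seronegative against seropositive subjects is planned. The tables by age group each use a single definition. Only redness and swelling are affected: pain has no size threshold and the systemic reactions share one scale across ages. With 47 seronegatives, an artefact of one or two subjects is lost in the interval. All of this stands, and it limits the point to interpretation of two solicited reactions.

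It does not remove the point. Descriptive rates are the whole of the safety output, so what they count should be clear. The by-age tables are set out by randomised group and do not repair the by-serostatus ones.

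A reader might go further and infer that the by-serostatus rates are confounded with age, with seronegatives bound to show more redness and more Grade 3. One could argue that never-exposed subjects tend to be younger in an endemic country, and that is plausible. But the documents give no age-by-serostatus breakdown, and Step 3 shows that the artefact vanishes when the shares match and reverses when seronegatives include fewer children. No rates at 50 mm or 100 mm are available to size a Grade 3 effect.

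**Conclusion.** The point holds for the pooled and by-serostatus tables of redness and swelling. Each mixes two definitions, at about 25% and 75% of subjects by design for the all-ages table, and this follows from the SAP text without any assumption about reaction rates. The size of the gap between the reported rate and either clean definition does rest on assumed rates; in the illustrations the reported rate is 1.5 to 2 times the rate at 25 mm or more, and 40% to 50% of the rate for any reaction.

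Distortion of the serostatus description is a possibility, not an established fact. It needs the share aged 9-11 to differ between the 47 and the 629, and that share is unreported. Nor do the documents support reading this as a flaw in the randomised comparison: stratification on age gives both groups the same mix. No primary endpoint or non-inferiority test is touched. It is a modest reporting weakness with an inexpensive remedy.

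**What to change.** In SAP 4.4.1.1:
- Keep the protocol's age-specific scales.
- For the all-ages and by-serostatus tables, add redness and swelling rows on common cut-offs for every subject, derived from the recorded millimetre sizes: at least above 0 mm and 25 mm or more, plus one common cut-off for large reactions.
- State that presence and Grade 3 on the age-specific scales are not comparable between 9-11 years and older subjects.
- Tabulate age group by serostatus. If the mix differs, show the by-serostatus rates within 9-11 years and within 12 years and over. Common cut-offs remove the artefact of definition, but not any real dependence of reaction size on age.
- Correct the title of Table 4.2, which refers both to subjects of 12 and over and to all subjects.

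The cost is SAP wording, a re-derivation from data already held and a few extra table rows. Rates above 0 mm in subjects of 12 and over will look higher than their protocol-scale rates wherever smaller reactions were recorded, which a footnote can explain.
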